7.1.1.7. Vital Signs

Vital signs will include blood pressure, heart rate, respiratory rate, and body temperature and will be assessed after the subject has been resting in the sitting position for at least 3 minutes.

7.1.1.8. Performance Status

This assessment must be performed during the screening assessments as well as the day of the first study treatment and prior to the first dose. Subsequent assessments will be performed as per the Schedule of Assessments (Appendix 1).

The ECOG and KPS performance indices are provided in Appendix 2.

7.1.2. Laboratory

7.1.2.1. Hematology

Hematology parameters will include a complete blood count including platelets and differential.

7.1.2.2. Chemistry (Serum)

Serum chemistry parameters will include sodium, potassium, chloride, blood urea nitrogen (BUN), creatinine, glucose, calcium, total protein, albumin, AST, ALT, alkaline phosphatase, total bilirubin, lactate dehydrogenase (LDH), phosphate, uric acid, magnesium and bicarbonate. Baseline TSH will also be required. If TSH is abnormal, further evaluation of serum T3, T4 will be at investigator's discretion.

7.1.3. Diagnostics/Procedures

7.1.3.1. Urinalysis

Urinalysis includes pH, ketones, specific gravity, bilirubin, protein, blood, and glucose.

7.1.3.2. Pregnancy Test

Serum or urine pregnancy test will be required at Screening by local laboratory only for women of childbearing potential. A serum or urine pregnancy test will also be performed on Day 1 prior to first dose. If positive, pregnancy must be ruled out by ultrasound to be eligible.

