4.1. Inclusion Criteria

To be enrolled in the study, each potential subject must satisfy all of the following inclusion criteria.

Disease Related

Metastatic renal cell cancer patients (any histologic subtype) with measurable and/or evaluable disease who have completed at least one line of prior systemic therapy are potentially eligible for this trial. Any number of prior systemic therapies are allowed, including prior nivolumab.

Laboratory

1. Adequate hematologic function defined as:
 - Absolute neutrophil count $>750 \text{ cells/mm}^3 (0.75 \times 10^9/\text{L})$.
 - Platelet count $>50,000 \text{ cells/mm}^3 (50 \times 10^9/\text{L})$.
 - Hemoglobin $>8.0 \text{ g/dL}$.
2. Adequate hepatic and renal function defined as:
 - Serum aspartate transaminase (AST) or alanine transaminase (ALT) $\leq 3.0 \times$ upper limit of normal (ULN).
 - Estimated Creatinine Clearance $\geq 30 \text{ ml/min}$ (Cockcroft-Gault)
 - Bilirubin $\leq 1.5 \times$ ULN (unless bilirubin rise is due to Gilbert's syndrome or of non-hepatic origin)
3. PT/INR $<1.5 \times$ ULN and PTT (aPTT) $<1.5 \times$ ULN.

Demographic

4. Men and women ≥ 18 years of age.
5. Eastern Cooperative Oncology Group (ECOG) performance status of 0-2.

Ethical/Other

6. Female subjects who are of non-reproductive potential (ie, post-menopausal by history - no menses for ≥ 1 year; OR history of hysterectomy; OR history of bilateral tubal ligation; OR history of bilateral oophorectomy). Female subjects of childbearing potential must have a negative serum pregnancy test upon study entry.
7. Male and female subjects who agree to use both a highly effective methods of birth control (eg, implants, injectables, combined oral contraceptives, some intrauterine devices [IUDs], sexual abstinence, or sterilized partner) and a barrier method (eg, condoms, cervical ring, sponge, etc) during the period of therapy and for 30 days after the last dose of study drug

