7. STUDY EVALUATIONS

7.1. Description of Procedures

A cycle has a duration of 28 days throughout this study.

All screening clinical and laboratory assessments must be performed within 28 days of Study Day 1 and prior to the first dose of study treatment.

All study tests and procedures should be evaluated at the study center at which the subject was enrolled.

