8. STUDY PROCEDURES

8.1. Screening Phase

Screening procedures will be performed up to 28 days prior to the first dose of study treatment, unless otherwise specified. Obtain written informed consent as indicated by subject's signature on the IRB approved ICF.

- Informed Consent
- Medical history
- Review of eligibility criteria
- Review and recording of all current, ongoing medications and any medications taken within 30 days prior to start of study medication (including over-the-counter drugs, vitamins and herbs)
- Complete physical exam including height and weight
- Vitals signs (including blood pressure, heart rate, respiratory rate, and body temperature)
- Performance Status
- CT/MRI scan
- 12-lead ECG. Subjects should be in a supine position and resting for at least 10 minutes before obtaining the ECG.
- Archival specimen
- Urine test
- Pregnancy Test
- Blood for translational studies
- Urine for translational studies
- Creatinine Clearance (measured or calculated)
- Laboratory tests for:
 - Hematology including differential
 - Serum chemistries (including TSH)
 - Serum pregnancy test (for women of childbearing potential only)
 - PT/INR and PTT

- Hepatitis serologies
- Confirm eligibility – complete enrollment checklist prior to enrollment

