8.2.1. Cycle 1, Day 1 Visit

Following completion of the Screening Visit and once eligibility has been confirmed, subjects are enrolled. Enrollment should occur as close to the time of the expected first dose as possible.

- Confirm eligibility criteria
- Review of current medications and any new medications since screening visit
- Review of current signs/symptoms including any new untoward events since screening
- Complete physical exam and weight
- Vital signs
- Performance status
- Pregnancy Test
- Laboratory tests for:
 - Hematology including differential
 - Serum chemistry
- Dose administration – ibrutinib
- Dose administration – nivolumab
- Provide drug diary and dosing instructions to subject
- Dispense study drugs

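### Section 7.1.3.2 accepts a urine test at Screening and names only ultrasound after a positive test, against the negative serum test in 4.1 item 6; separately, no pregnancy test is scheduled after Cycle 1 Day 1

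*Combined protocol and SAP*

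**What the plan says.** **Entry rule.** Section 4.1 item 6 states: "Female subjects of childbearing potential must have a negative serum pregnancy test upon study entry". It offers no urine alternative and no ultrasound exception. Section 8.1 lists, among the Screening laboratory tests, "Serum pregnancy test (for women of childbearing potential only"; a general pregnancy-test bullet, with no type given, also appears there.

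**Procedure rule.** Section 7.1.3.2 says: "Serum or urine pregnancy test will be required at Screening by local laboratory only for women of childbearing potential". It continues: "A serum or urine pregnancy test will also be performed on Day 1 prior to first dose". It then closes with "If positive, pregnancy must be ruled out by ultrasound to be eligible". It does not say whether that last sentence covers the Screening test, the Day 1 test or both.

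**Timing.** Section 7.1 says: "All screening clinical and laboratory assessments must be performed within 28 days of Study Day 1". Appendix 7 allows registration up to 72 hours before treatment, with the eligibility checklist completed beforehand. The Cycle 1 Day 1 list in 8.2.1 includes "Confirm eligibility criteria" and a pregnancy test of unstated type.

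**After Day 1.** The visit lists in 8.2.2 to 8.2.8 and the follow-up list in 8.3 contain no pregnancy test. The Appendix 1 row has two marks, which match Screening and Cycle 1 Day 1.

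**Consequences of pregnancy.** Pregnancy is exclusion 15 in 4.2 and a reason to stop treatment in 9.2. Section 11.4.3 requires immediate discontinuation and asks the subject to tell the investigator at once. Item 7 of 4.1 requires a highly effective method plus a barrier method of contraception "during the period of therapy and for 30 days after the last dose of study drug".

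**The concern.** There are two separate issues.

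The first is a conflict in the entry rules. Sites that follow 7.1.3.2 and sites that follow 4.1 could decide differently about the same woman, or enrol her and record a deviation. The case that matters for safety is a woman whose Screening serum test was negative but whose Day 1 test is positive. If the older result is taken to satisfy item 6, the only instruction left is an ultrasound. The text gives no repeat serum test, no minimum interval and no second scan. An ultrasound done very early might not show a pregnancy.

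The second is a gap in monitoring. Section 1.3.2 reports fetal loss and malformations in rats, at roughly 6 and 14 times patient exposure. The stopping rule in 11.4.3 can act only on a pregnancy that someone has noticed, and after Day 1 no scheduled test would notice one. The combination may run for a year, and 3.2.1 gives ibrutinib no fixed end date.

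**Working it through.** The plan gives no figure to reproduce. The main check is a comparison of text, followed by a rough estimate of size.

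**1. Entry rules side by side**

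| Situation | 4.1 item 6 | 8.1 | 7.1.3.2 |
|---|---|---|---|
| Test type at Screening | Serum | Serum listed | Serum or urine |
| Urine negative, no serum test done | Not met | Listed serum test missing | Met |
| Serum positive, ultrasound clear | Not met | Silent | Can be eligible |

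The second and third situations give opposite answers in 4.1 and 7.1.3.2. Section 8.1 agrees with 4.1 on test type. A clear ultrasound may satisfy exclusion 15, but it does not produce the negative serum result that item 6 demands.

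**2. Scheduled tests**

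Screening and Cycle 1 Day 1 each have one. Cycle 1 Day 15 through End of Treatment and follow-up have none. Serum chemistry is already drawn on Day 1 of Cycle 2 (8.2.3), Day 1 of Cycles 3 to 7 (8.2.5), Cycle 8 onward (8.2.7) and at End of Treatment (8.2.8).

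**3. Size of the entry gap**

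None of these inputs is in the documents except the total of 30 patients and the 28-day Screening limit. All the others are assumptions.

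- N, women of childbearing potential among 30 patients: 0 to 3.
- r, conceptions per woman-year before Day 1: 1% to 10%. Item 7 states its contraception period from the start of therapy, so it does not clearly cover this interval.
- w, days in which a test is positive but ultrasound is not. A test positive from 14 days after conception and ultrasound from 21 gives w = 21 − 14 = 7. A test positive from 10 days and ultrasound from 28 gives w = 28 − 10 = 18.

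Expected patients dosed after a positive Day 1 test and a falsely clear ultrasound = N × r × w / 365.

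- N = 0: 0.
- N = 3, low end: 3 × 0.01 × 7 / 365 = 0.0006, about 1 in 1,700 trials of this size.
- N = 3, high end: 3 × 0.10 × 18 / 365 = 0.015, about 1 in 70.

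The formula requires the gap between the Screening test and Day 1 to be at least w. If that gap is 7 days, the high end falls to 3 × 0.10 × 7 / 365 = 0.006. It also assumes that every such woman is dosed after a single scan with no repeat test, so these are upper values for given inputs.

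**4. Pregnancies on treatment**

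Assume 0.1% to 1% per woman-year with two contraceptive methods. Three women treated for a full year give 3 × 0.001 = 0.003 to 3 × 0.01 = 0.03. Many would be treated for less time: section 1.1.1 cites median progression-free survival of 2.7 to 4.2 months on nivolumab. Scaling by those durations gives 0.003 × 2.7/12 = 0.0007 to 0.03 × 4.2/12 = 0.0105.

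**The case against.** The strongest reply is that the protocol already prevents the harm. Section 4.1 requires every inclusion criterion to be met, and Appendix 7 item G bars registration of a patient who fails any requirement. Exclusion 15 stands, and eligibility is confirmed again on Day 1. The ultrasound sentence sets a necessary condition and nowhere says that it replaces item 6, so in practice it is a hold until the scan. The entry wording in item 6 can also be read as needing a current serum result. During treatment, two contraceptive methods and the duty to report pregnancy apply. The size estimate rests on assumed inputs and includes zero.

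Much of this stands. A reader might infer that the protocol lets pregnant women be dosed, or that ultrasound overrides the serum criterion. The documents do not support either reading. A reader might also infer that the missing later tests break a promise made elsewhere. They do not, because no section commits to testing on treatment, and 11.4.3 supplies a detection route through the subject's own report.

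What the reply does not remove is the mismatch itself. Two sections give opposite answers for a positive serum test with a clear scan, and 7.1.3.2 admits a urine test where 4.1 and 8.1 call for serum. The Day 1 re-check and exclusion 15 add limited protection, because the same ultrasound may be what settles whether she is pregnant. Self-report also works only once the woman herself suspects a pregnancy.

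**Conclusion.** The point holds as an inconsistency in the entry rules plus a separate gap in monitoring. It concerns subject safety at low frequency. With three women of childbearing potential, the entry gap amounts to 0.0006 to 0.015 patients per trial. Pregnancies on treatment amount to 0.003 to 0.03 per year of treatment for the three women together. Both are zero if no such woman enrols. These figures depend wholly on the assumed number of women, conception rates and test timings, and the first also on the reading that a Screening serum result up to 28 days old still satisfies item 6. The textual conflict and the empty schedule do not depend on any of these assumptions. Nothing here touches the sample size, the progression-free survival endpoint or its analysis. It is worth correcting at the next amendment because the hazard is one the protocol itself describes and the correction is cheap.

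**What to change.** **1. Section 7.1.3.2.** Require a serum test at Screening and keep serum or urine on Day 1 before the first dose. Replace the ultrasound sentence with:

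> After any positive test both drugs are withheld and the subject may start only if a subsequent serum test is negative, as required by 4.1 item 6; ultrasound does not replace the serum test.

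Keeping the Day 1 test here as a condition for dosing, and not adding it to item 6, avoids a clash with Appendix 7, where the checklist is completed before registration.

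**2. Appendix 1 and sections 8.2.3, 8.2.5, 8.2.7 and 8.2.8.** For women of childbearing potential, add a pregnancy test on Day 1 of Cycle 2 and of each later cycle, and at End of Treatment, using blood already drawn for chemistry. If it is positive, withhold both drugs and confirm by serum test. If pregnancy is confirmed, apply 11.4.3.

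**Cost.** One edit to 7.1.3.2, one row of Appendix 1 and one line in each of four visit lists. A year holds 13 cycles of 28 days (13 × 28 = 364), so Cycles 2 to 13 plus End of Treatment give 12 + 1 = 13 assays per woman, or 39 for three women, with no extra blood draw. The number rises if ibrutinib continues beyond a year.

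**Downside.** A woman with a persistently false-positive serum test could not enrol, which item 6 already implies. A false positive arising on treatment would hold both drugs until resolved; section 9.2 allows 4 weeks for ibrutinib and 42 days for nivolumab before discontinuation applies. An exception that cleared such women by repeated ultrasound is not advised. It would rest on assumed timings, could delay treatment of metastatic cancer, and would leave the same woman testing positive again at Cycle 2.

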7.1.3.3. ECG

ECGs should be performed at screening and subsequently at the investigator's discretion, particularly in subjects with arrhythmic symptoms (eg, palpitations, lightheadedness) or new onset dyspnea.

Subjects should be in supine position and resting for at least 10 minutes before study-related ECGs. During visits in which both ECGs and blood draws are performed, ECGs should be performed first. Abnormalities noted at Screening should be included in the medical history.

7.2. Efficacy Evaluations (Histology Specific)

Archival specimens will be obtained at screening within 28 days before the first dose of ibrutinib and nivolumab.

7.3. Sample Collection and Handling

The actual dates and times of sample collection must be recorded in source documents for transcription to the CRF or laboratory requisition form. Refer to the Schedule of Assessments (Appendix 1) for the timing and frequency of all sample collections.

8. STUDY PROCEDURES

8.1. Screening Phase

Screening procedures will be performed up to 28 days prior to the first dose of study treatment, unless otherwise specified. Obtain written informed consent as indicated by subject's signature on the IRB approved ICF.

- Informed Consent
- Medical history
- Review of eligibility criteria
- Review and recording of all current, ongoing medications and any medications taken within 30 days prior to start of study medication (including over-the-counter drugs, vitamins and herbs)
- Complete physical exam including height and weight
- Vitals signs (including blood pressure, heart rate, respiratory rate, and body temperature)
- Performance Status
- CT/MRI scan
- 12-lead ECG. Subjects should be in a supine position and resting for at least 10 minutes before obtaining the ECG.
- Archival specimen
- Urine test
- Pregnancy Test
- Blood for translational studies
- Urine for translational studies
- Creatinine Clearance (measured or calculated)
- Laboratory tests for:
 - Hematology including differential
 - Serum chemistries (including TSH)
 - Serum pregnancy test (for women of childbearing potential only)
 - PT/INR and PTT

- Hepatitis serologies
- Confirm eligibility – complete enrollment checklist prior to enrollment

8.2. Treatment Phase

Treatment with ibrutinib in combination with nivolumab will continue for a maximum of one year or until 1) tumor progression; 2) unacceptable or intolerable toxicity; 3) patient withdrawal for any reason; 4) physician choice if in the best interest of the patient. Treatment with Ibrutinib will continue until either disease progression, or physician choice, or patient choice, or unacceptable or intolerable toxicities. Investigator discretion as to continuing single agent nivolumab for a maximum of one year will be allowed for patients who are unable to receive the doublet due to toxicity or patient preference.

8.2.1. Cycle 1, Day 1 Visit

Following completion of the Screening Visit and once eligibility has been confirmed, subjects are enrolled. Enrollment should occur as close to the time of the expected first dose as possible.

- Confirm eligibility criteria
- Review of current medications and any new medications since screening visit
- Review of current signs/symptoms including any new untoward events since screening
- Complete physical exam and weight
- Vital signs
- Performance status
- Pregnancy Test
- Laboratory tests for:
 - Hematology including differential
 - Serum chemistry
- Dose administration – ibrutinib
- Dose administration – nivolumab
- Provide drug diary and dosing instructions to subject
- Dispense study drugs

8.2.2. Cycle 1, Day 15 Visit

- Review of concomitant medications
- Review of adverse events
- Review returned subject dosing diary
- Physical exam
- Vital signs
- Performance Status
- Blood for translational studies
- Urine for translational studies
- Lab sample collection for
 - Hematology
 - Serum chemistry

8.2.3. Cycle 2, Day 1 Visit

- Review of concomitant medications
- Review of adverse events
- Review returned subject dosing diary and dispense new diary
- Physical exam
- Vital signs
- Performance Status
- Lab sample collection for
 - Hematology
 - Serum chemistry

8.2.4. Cycle 2, Day 15 Visit

- Review of concomitant medications
- Review of adverse events
- Review returned subject dosing diary
- Physical exam
- Vital signs
- Performance Status
- Lab sample collection for
 - Hematology including differential

8.2.5. Cycle 3-7, Day 1 Visit

- Review of concomitant medications
- Review of adverse events
- Review returned subject dosing diary and dispense new diary
- Physical exam
- Vital signs
- Performance Status
- Disease assessment
- Lab sample collection for
 - Hematology including differential
 - Serum chemistry

8.2.6. Cycle 3- 7, Day 15 Visit

- Review of concomitant medications
- Review of adverse events
- Vital signs
- Lab sample collection for
 - Hematology including differential

8.2.7. Cycle 8 and Beyond

- Review of concomitant medications
- Review of adverse events
- Review returned subject dosing diary and dispense new diary
- Disease assessment
- Lab sample collection for
 - Hematology including differential
 - Serum chemistry

8.2.8. End of Treatment (EOT) Visit

- Review of concomitant medications
- Review of adverse events
- Blood for translational studies
- Urine for translational studies
- Lab sample collection for
 - Hematology including differential
 - Serum chemistry

8.3. Follow-up Phase

Once a subject has completed the End-of-Treatment Visit they will enter the Follow-up Phase. Once subjects experience TF, relapse, or start use of alternative anticancer therapy (for subjects who have not withdrawn consent), they will be contacted approximately every 3 months (± 14 days) by clinic visit or telephone until death, subject withdrawal, lost to follow-up, study termination by the study sponsor, or up to 6 months whichever occurs first.

- Survival status, including other malignancies
- Subsequent anticancer therapy

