9.2. Withdrawal from Study Treatment

Study treatment will be discontinued in the event of any of the following events:

1. Unacceptable toxicity
2. Treatment failure or no evidence of clinical benefit per investigator assessment
3. An intercurrent illness or adverse event that prevents further ibrutinib administration.

4. Withdrawal of consent for treatment by subject
5. Investigator decision (such as chronic noncompliance, significant protocol deviation, or best interest of the subject)
6. Study termination by Pharmacyclics or study sponsor
7. Subject becomes pregnant
8. Nivolumab is held for greater than 42 days (the subject can stay on study with Ibrutinib only)
9. Ibrutinib is held for greater than 4 weeks. If Ibrutinib therapy is held for greater than 4 weeks, then the subject must discontinue from the nivolumab as well

All subjects, regardless of reason for discontinuation of study treatment will undergo an End of Treatment Visit and be followed for treatment failure and survival.

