10.3. Sample Size Determination

In the RECORD-1 trial, PFS at 6 months was approximately 40%. Assuming that the ibrutinib plus nivolumab combination will increase the PFS rate from 40 to 70% at the 6 month timepoint, a sample size of 25 patients will provide 90% power and one-sided level 0.034 to detect this difference, with a critical value of 15 or more patients out of 25 experiencing PFS at 6 months. To account for dropouts, a total of 30 patients will be accrued. Efficacy analysis will be performed on all patients enrolled in the study regardless of dose level assignment; i.e., patients from each of the completed dose levels will be pooled as described in the study schema.

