10.5. Statistical Methods

Primary endpoint: Progression-free survival (PFS) as the number of months from baseline to death or progression, defined in Appendix 4. The duration of PFS will be summarized descriptively using Kaplan-Meier survival plots and life tables. The number and proportion with PFS of 6 months or more will be reported, adjusting for censoring using the life-table approach. If the number with PFS at least six months is 15 or more out of 25 evaluable patients, this will constitute evidence supporting an improvement over historic PFS rates.

Secondary endpoints: RECIST response will be calculated as in Appendix 4, and will be summarized by the number and percentage of patients, accompanied by 2-sided exact 95% confidence intervals. Overall survival will be summarized descriptively by Kaplan-Meier curves and life table estimates, as for PFS. Number and type of adverse events will be summarized descriptively by system organ class affected and by grade of event, overall and by dose. Vital signs and laboratory test results will be summarized descriptively (mean, SD, range) overall and by dose.

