14. APPENDICES

Appendix 1. Schedule of Assessments

Study Visits	Screening Phase	Treatment Phase (1 cycle = 28 days)							Suspected PD	End-of-Treatment ^a	FU ^b
		Cycle 1		Cycle 2		Cycles 3–7		Cycles 8 and beyond			
		D1 (baseline)	D15	D1	D15	D1	D15	D1			
Study Visit Windows	-28 days			± 3 days					Any time	30 days after treatment d/c	q 3 mos
Informed consent	X										
Confirm eligibility	X	X									
Medical history	X										
Review concomitant medications	X	X	X	X	X	X	X	X		X	
Review adverse events ^c			X	X	X	X	X	X		X	
Study drug compliance review ^d			X	X	X	X		X			
Height	X										
Physical exam, vital signs, weight, ECOG	X	X	X	X	X	X		X	X	X	X
Disease assessment [†] :											
CT/MRI scan	X					X		X	X		X
Overall response assessment						X		X	X		X
Hematology	X	X	X	X	X	X	X	X	X	X	
Serum chemistry [*]	X	X	X	X		X		X	X	X	
TSH ^f	X	X				X		X		X	
Creatinine clearance (Cockcroft-Gault)	X									X	
PT/INR and PTT	X										
Hepatitis serologies	X										
Pregnancy test	X	X									
12 lead ECG	X	As clinically indicated [‡]									
Urine test	X										
Archival Specimen	X										
Blood for Translational Studies ^e	X		X							X	
Urine for Translational Studies	X		X							X	
Any new anticancer therapy											X
Study Drug Administration											
Nivolumab infusion		Every 2 weeks									
Ibrutinib (continuous)		X	X	X	X	X	X	X			

Abbreviations: D = day; d/c = discontinuation; PD = progressive disease; FU = follow-up, TSH = thyroid stimulating hormone.

Nivolumab: 240 mg IV every 2 weeks

[†]Disease assessment to be performed every 8 weeks

*Laboratory testing prior to Nivolumab treatment (will be done before every 2 doses of Nivolumab treatment, every 4 weeks).

[‡]ECG's may be performed at the investigator's discretion, particularly in subjects with arrhythmic symptoms (eg, palpitations, lightheadedness) or new onset dyspnea

a. An EOT visit will occur 30 ± 7 days from the last dose of study drug or prior to the start of a new anticancer treatment.

b. Once subjects experience TF, relapse, or start use of alternative anticancer therapy (for subjects who have not withdrawn consent), they will be contacted approximately every 3 months (±14 days) by clinic visit or telephone until death, subject withdrawal, lost to follow-up, study termination by the study sponsor, or up to 6 months whichever occurs first.

c. AEs are reported from the time the patient signs the Informed Consent Form until 30 days following last dose of study drug.

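### For patients who stop treatment without progression, Section 8.3, the Appendix 1 follow-up column and the 8-week footnote disagree on imaging, so progression before month 6 may be found late and counted as a 6-month success

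*Combined protocol and SAP*

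**What the plan says.** Section 10.5 defines "Progression-free survival (PFS) as the number of months from baseline to death or progression", so follow-up for the endpoint does not end with treatment. The decision rule there is a count: 15 or more of 25 evaluable patients with PFS of at least six months. Section 9.2 says that everyone who stops, for whatever reason, has an end-of-treatment visit and will "be followed for treatment failure and survival". It gives neither method nor interval.

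Imaging after treatment stops is addressed in four places:

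- **Section 8.2.8 and the Appendix 1 end-of-treatment column:** no disease assessment. The visit covers medications, adverse events, laboratory tests and translational samples.
- **Section 8.3:** only survival status and subsequent therapy are listed. The 3-monthly contact, which may be by telephone, applies "Once subjects experience TF, relapse, or start use of alternative anticancer therapy".
- **Appendix 1, follow-up column:** CT/MRI and overall response are marked, but the column is headed three-monthly and footnote b repeats the trigger of Section 8.3.
- **Appendix 1, footnote to the disease-assessment row:** "Disease assessment to be performed every 8 weeks", with no limit to the treatment phase.

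Appendix 1 also has a suspected-progression column that allows a scan at any time. Appendix 4 asks sites to try to document objective progression after discontinuation in patients with symptomatic deterioration.

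**The concern.** Take a patient who stops both drugs for toxicity at week 10 with stable disease. The contact in Section 8.3 depends on the very event that it would have to detect, so the text of that section gives this patient no scheduled look for progression. The follow-up column gives a scan every 3 months, and the row footnote gives one every 8 weeks. Sites can reasonably differ.

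The affected patients are in the primary analysis. The evaluable population in Section 10.4.2 requires only one completed cycle, and item 9 of Section 9.2 ends nivolumab too when ibrutinib is held for more than 4 weeks. If progression before month 6 goes unseen until after month 6, the patient may enter the count as a success. Toxicity would then push the efficacy count upward, in a single-arm trial with no control arm to share the bias.

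**Working it through.** **1. The plan's own figure.** Section 10.3 assumes that the combination "will increase the PFS rate from 40 to 70% at the 6 month timepoint", and states that "a sample size of 25 patients will provide 90% power and one-sided level 0.034 to detect this difference". With X binomial (25, p):
- P(X ≥ 15 | p = 0.40) = 0.0344, stated as 0.034.
- P(X ≥ 15 | p = 0.70) = 0.902, stated as 90%.

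Both reproduce, provided month-6 status is known without error.

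**2. Timing on the 3-monthly reading.** Six months is 26.1 weeks, three months is 13.0 weeks, and the end-of-treatment visit is 30 days (30/7 = 4.3 weeks) after last dose. The documents do not say where the 3 months start. The latest stopping time that still gives a scheduled scan by month 6 is:
- counted from the end-of-treatment visit: 26.1 − 13.0 − 4.3 = week 8.8 (6.8 to 10.8 with the ±14-day window);
- counted from last dose: 26.1 − 13.0 = week 13.1 (11.1 to 15.1).

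For the patient who stops at week 10, the first follow-up scan falls at 10 + 4.3 + 13.0 = week 27.3, after month 6, or at 10 + 13.0 = week 23.0, before it. Continued 8-weekly scanning would give scans at weeks 16 and 24.

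**3. Effect on the rule.** The documents give no stopping rate, share of deaths or PFS shape. Assumptions: exponential PFS with a true 6-month rate of 40%; 30% of events are deaths, dated exactly; stopping times uniform over weeks 4 to 20; no unscheduled scans; progression found after month 6 counts as a success.

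The 8-weekly baseline can be checked by hand. The hazard is −ln(0.40)/26.1 = 0.0351 per week, so PFS at week 24 is exp(−0.0351 × 24) = 0.431. Non-fatal progressions between week 24 and month 6 are missed: (0.431 − 0.400) × 0.7 = 0.021. The apparent rate is 0.421 and P(X ≥ 15) = 0.055. That gap belongs to any 8-weekly schedule, so only the excess over 0.055 belongs to this point.

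Simulated apparent 6-month rate, then P(X ≥ 15 of 25):

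| Scans after stopping | 15% stop without detected progression | 22% stop |
|---|---|---|
| every 8 weeks | 0.421 → 0.055 | 0.421 → 0.055 |
| 3-monthly from last dose | 0.438 → 0.076 | 0.446 → 0.089 |
| 3-monthly from end-of-treatment visit | 0.447 → 0.091 | 0.460 → 0.114 |
| none, read as progression-free | 0.469 → 0.133 | 0.493 → 0.191 |

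**4. A second set of assumptions.** With a constant stopping hazard (10%, 20% or 30% stopping by week 26), no separate deaths, and the shift relative to 8-weekly scanning added to 0.40, the probability moves from 0.034 to 0.041–0.064 with 3-monthly scans and to 0.057–0.143 with none. The direction is the same; the 3-monthly effect is smaller.

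**The case against.** The strongest reply is that Appendix 1 already provides 8-weekly scans after treatment. The treatment columns from Cycle 3 are Day 1 of each 28-day cycle, yet the row footnote sets scans at 8 weeks. If the footnote overrides the column frequency there, it can override the three-monthly heading too. This stands as a live reading, and the point is therefore a conflict between passages. A reader might infer that the plan takes these patients off 8-weekly imaging, so that their progressions are found after month 6 or never. The documents do not support that: the footnote is not limited to treatment, early stoppers can have a 3-monthly scan before month 6, and a suspected-progression scan is allowed at any time. If such scans caught half of the otherwise late progressions, the 0.091 above would fall to about 0.07 (apparent rate (0.421 + 0.447)/2 = 0.434). Scans driven by symptoms do not, however, replace scheduled imaging for silent progression.

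Second, toxicity need not end treatment. Sections 3.2.1 and 8.2 allow nivolumab alone, and item 8 of Section 9.2 allows ibrutinib alone; those patients keep their on-treatment scans. This reduces the number affected, although item 9 limits it.

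Third, scoring as a success is an assumption. Section 10.5 reports the 6-month proportion with life-table adjustment for censoring, and Section 10.3 accrues 30 patients to cover dropouts from 25, so such patients might be censored or replaced. That also stands. But the count of 15 in 25 carries no censoring rule, so nothing prevents the favourable scoring.

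**Conclusion.** The point holds as an unresolved conflict that bears on the primary decision rule. No passage plainly keeps a patient who stops without progression on 8-weekly imaging, and two of the three readings can leave that patient without a scheduled scan before month 6. The likely direction is a more favourable count. The illustrated size, against 0.055 with continued 8-weekly scans, is 0.08 to 0.09 (3-monthly) or 0.13 (none) at 15% stopping, and 0.09 to 0.11 or 0.19 at 22%.

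No single error rate should be quoted in place of the stated 0.034. The figures depend on the assumed stopping rate, death share and exponential PFS, on where the 3 months start, on no suspected-progression scans being done, and on late-found progressions being scored as progression-free. The documents settle none of these. The case for the change rests on the conflict and its low cost, more than on any one figure.

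**What to change.** Reconcile Section 8.3, the Appendix 1 follow-up column and footnote b with the 8-week footnote, for example: *Patients who stop study treatment for any reason other than progression continue CT/MRI every 8 weeks, counted from Cycle 1 Day 1, until RECIST progression, death, new anticancer therapy or withdrawal of consent.* Limit the 3-monthly contact to patients who have progressed or started new therapy.

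In Section 10.5, state that a patient without a scan confirming progression-free status at month 6, including one who has moved to new therapy, is not counted as a success in the rule of 15 in 25, and report the life-table estimate alongside. Name the scan that serves for month 6, since the 8-weekly grid falls at weeks 24 and 32.

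The cost is about one to three extra scans before month 6 for each affected patient, and a slightly less favourable count. The sample size does not change.
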